17.3 Sponsor Records

Tornier will maintain the following accurate, complete, and current records relating to this investigation:

- All correspondence with an investigator, an IRB, or FDA, including required reports.
- Records of shipment and disposition. Records of shipment shall include the name and address of the consignee, type and quantity of device, date of shipment, and batch number or code mark. Records of disposition shall describe the batch number or code marks of any devices returned to Tornier, repaired, or disposed of in other ways by the investigator or another person, and the reasons for and method of disposal.
- Signed investigator agreements including the financial disclosure information required to be collected under 812.43(c) (5).
- Records concerning adverse events.

17.4 Sponsor Reports

Report	Submit to:	Description/Constraints
UADE Evaluations	FDA, all participating	10 working days after the sponsor first
	IRBs	receives notice of the effect. Thereafter,
		Tornier shall submit such additional reports
		concerning the effect as FDA requests.
Withdrawal of IRB	FDA, all reviewing IRBs	Within 5 working days after receipt of notice
approval	and participating investigators	of the withdrawal of approval.
Withdrawal of FDA	All reviewing IRBs and	Within 5 working days after receipt of notice
approval	participating investigators	of the withdrawal of approval.
Current investigator list	FDA	Tornier shall submit, in 6 month intervals, a current list of the names and addresses of all investigators participating in the investigation.
Progress Reports	FDA and all reviewing IRBs	At regular intervals, at least yearly
Recall and device	FDA and all reviewing	Any request that an investigator return, repair,
disposition	IRBs and participating	or otherwise dispose of any unit of a device
	investigators	shall be reported within 30 working days after
		the request is made and shall state why the
		request was made.
Completion or termination of the investigation	FDA	Within 30 working days
Final Report	FDA and all reviewing	Within 6 months of study termination.
	IRBs and participating	
	investigators	
Informed Consent	FDA	Within 5 working days of receipt of notice of
		device use without obtaining informed consent.
Other	FDA, reviewing	Provide accurate, complete and current
	IRB/MEC	information about any aspect of the
		investigation as requested at any time.

Table 7: Sponsor Reporting Requirements

18 Publications

Tornier will form a Publication Committee to manage publications that utilize data from this study. The committee will develop a publication plan outlining the details related to primary, secondary, and ancillary publications and authorship rules. The responsibilities of the committee will include reviewing publication ideas and proposals, providing input on their scientific merit and clinical relevance, and prioritizing them accordingly. Membership in the publication committee or participation as an investigator in this study does not guarantee authorship. Publication Committee membership criteria will be established and documented by Tornier.

Primary study results will be published following the final study analyses.

The International Committee of Medical Journal Editors (ICMJE) authorship guidelines will be used. The ICMJE guidelines require the conditions below are met to be included as an author:

- Substantial contribution to conception and design, or acquisition of data, or analysis and interpretation of data
- Drafting the article or revising it critically for important intellectual content
- Final approval of the version to be published

This study will be registered in www.clinicaltrials.gov, and results will be posted.

Appendix 2 Strength Testing Protocol

The Constant Score

This test will be administered according to a modification of the standard procedure established in the updated paper by Constant, et al. in the *Journal of Shoulder and Elbow Surgery*, 2008 [2].

Further modifications to the described procedure for this test are related only to the use of equipment:

- 1) For the strength component of the score, a fixed force gauge as depicted in Figure 6 will be used.
- 2) For Visual Analog Scales (VAS), either a paper form with a graduated line or the study electronic database, will be used.

Strength (Power) Measurement

A fixed force gauge is a device for measuring force, moment of force (torque), or power. It is used in shoulder orthopedics for measuring the arm strength of patients to evaluate physical status, performance and task demands.

Figure 6: Fixed Force Gauge

Method

The evaluation method for this study will be performed using the fixed force gauge device supplied or approved by Tornier and a modification of the standard methods as described below [2]

- The assessment will use a fixed force gauge as depicted in the photograph above.
- The test position is the subject standing with the arm in 90° elevation in the scapular plane, elbow extended and forearm pronated. An adjustable strap is placed around the forearm just proximal to the radio carpal joint and attached to the fixed force gauge.
- The fixed force gauge is firmly secured by the examiner. The subjects are instructed to pull upward with maximum effort until requested to stop.
- The reading of the fixed force gauge is taken after five seconds of maximum effort.
- At least one pull is required, but three are suggested. All measurements will be collected.
- Patients unable to reach the test position will receive the value of zero.

Appendix 3 Subject Rehabilitation Guidelines

You are being asked to follow specific guidelines during your post-study implant rehabilitation. Your doctor may provide you with more detailed instructions in addition to the study guidelines. The following instructions inform you when to start using passive and active motion. Passive motion is the use of an external force (e.g., other arm) to move your treated arm. DO NOT use your treated arm muscles during passive motion. Active motion is when you start using your muscles of the treated arm without assistance.

Below are general guidelines to keep in mind during your recovery.

- Wear the sling every night for at least the first 6 weeks.
- Push yourself up in bed or from a chair using your non-surgical arm.
- Follow your program of home exercises and don't do more than prescribed, as overuse of the shoulder can be harmful.
- No sports or heavy lifting for at least 4-6 months.
- Do not drive. Your doctor will let you know when it is safe to drive

After your surgery, you should limit your shoulder motion as follows

- Passive motion ONLY for up to 3 weeks.
- Limit forward elevation to 120 degree for the first 6-8 weeks. (Figure 1)
- Passive external rotation to the side should be limited to 30 degrees (Figure 2).
- At 3-4 weeks you may begin active assistive motion. During this phase you should begin using your treated shoulder muscles along with assistance (similar to the passive phase).
- At 6-8 weeks you may begin active motions without assistance. Limit external rotation to 45 degrees and internal rotation to L5. (Figure 3)
- Isometric strengthening phase may be initiated at 3 months.
- Do not begin any vigorous strengthening until 20 weeks after surgery.

[figure not shown]
[figure not shown]

Figure 1: Active assisted Forward Elevation

[figure not shown]

Figure 3: Internal Rotation

Images adapted from http://shoulderarthritis.blogspot.com/2011_03_01_archive.html

- Antiseptic: A germicide that is used on skin or living tissue for the purposes of inhibiting or destroying microorganisms.
- Decontamination: A process or treatment that renders a medical device, instrument, or environmental surface safe to handle. Ranges from sterilization to cleaning with soap and water.
- Disinfectant: A germicide that is used solely for destroying microorganisms on inanimate objects.
- Disinfection: Generally less lethal than sterilization. It eliminates virtually all recognized pathogenic microorganisms but not necessarily all microbial forms on inanimate objects. It does not ensure overkill.
- Sterilization: Use of a physical or chemical procedure to destroy all microbial life; including large numbers of highly resistant bacterial endospores.

4. Procedures for Retrieval, Handling, and Packaging

Any part of the Tornier Flex Shoulder System with a Pyrocarbon humeral head that is removed from a study subject must be returned to Tornier for analysis.

Please contact Tornier Clinical Department to request a Return Material Authorization number (RMA) which details return instructions.

The following steps are important and necessary to aid in the analysis of an explanted device:

4.1. Pre-explant functional check:

• Whenever possible, a pre-explant functional check of the implant is recommended to assist in post-explant analysis. Objective measurements of shoulder function should be obtained when possible. These measurements include: American Shoulder and Elbow Surgeons Standardized Shoulder assessment (ASES),

Constant score, Single Assessment Numeric Evaluation (SANE), and shoulder satisfaction (since they were used as measures of the system's performance in this study) as well as other clinical indicators such as EQ5D, pain, tenderness, swelling, etc.

• A non-invasive examination of the implanted system via X-ray should be performed in accordance with the Pyrocarbon IDE Study protocol X-ray procedures.

4.2. Explant record

- If any components are misaligned in any way due to migration or surgical malpositioning at the time of revision surgery, then every effort should be made to mark the components prior to removal in order to preserve their in situ orientation. Ideally, the operating surgeon should be asked to make a small mark(s) with a fine osteotome at the 12 o'clock (mid-line) position on the CrCo double taper neck component before dismounting from stem. The metallic osteotome should not touch the Pyrocarbon bearing surface component, otherwise it could damage it. If the bearing surface is damaged, the position of the contact/damage on the Pyrocarbon bearing surface would be recorded. If the implants are not marked before extraction or immediately after, then the true location of the wear scars/features can only be guessed. If possible, photos of the marks made should be taken immediately after they are made. If the 12 o'clock position is not accessible and another marking position is used, photographic records as well as a written note of the position should be documented.
- Shortly after removal, a detailed record of any damage caused to the components during extraction should be documented, especially in the presence of the operating surgeon. Adequate macro photography can also be helpful. This information should be adequately labeled and should accompany the explanted components. This should facilitate the ability to differentiate between damaged regions caused in vivo and those caused during extraction.

5. Collection of clinical history of the implant and patient

Subject Information (data previously collected in Baseline CRF)

- Subject Identification Number
- Subject's height and weight
- Female/male
- Date of birth
- Number of previous surgeries prior to implantation of current device
- Known metal sensitivities

Initial Surgery Details (data previously captured in the initial Operative CRF)

- Original diagnosis
- Date of Implantation
- Hospital where implantation occurred
- Surgeon name
- Surgical site, left or right
- Implanted components (serial numbers, size, and reference numbers)

Revision/Explant Information (will be collected on revision/explant CRF)

- Date of removal
- Hospital where explant occurred
- Surgeon name
- Surgical site description
- Subject's height and weight at retrieval
- Reasons for device removal (primary clinical diagnosis)
- Tissue samples, descriptions or tissues, if applicable
- Description of how the device was removed
- Surgeon commentary/observations at revision, including assessment of bone quality if applicable
- Other mitigating factors, if applicable

Other Data Collected

- Length of follow-up (automatically calculated in database)
- Age at retrieval (automatically calculated in database)
- Any complications occurring during the removal procedure (Complete AE CRF)
- Any radiographs and/or other imaging available for analysis (Complete Imaging CRF)
- Patient activity, experience with implant, and clinical performance (complete QOL forms)

6. Collection of tissue and fluid samples near the implant,

Collection of tissue and fluids will depend on how invasive is the revision, and particularly whether the stem will be removed, and also whether a glenoid component will be implanted. Surgeons shall not remove more fluid or tissue than those necessary for the revision. Data will be collected as follows:

• Whenever it's possible and before opening articular capsule:

(a) Extraction of synovial fluid by puncturing the joint (ideally 1ml, 1 ml of physiological saline can be injected and recovered),

(b) extraction of 1ml blood (ideally decision made at the time of operation) each sample rapidly frozen and stored at - 20 °C to measure blood ion levels.

NOTE: Fluid samples should not be sent to Tornier. Analysis should be completed at the hospital, as appropriate.

- Extraction of a piece of articular capsule (minimum 1cm of length)
- Extraction of a portion of cartilage (in the glenoid side) with a form of "carrot" whenever it's possible (or another form), to analyze the bone cartilage interface and the cartilage status, by histological methods.
- If important black color is detected (presence of wear particles), additional portions of tissues should be extracted and placed into a separate solution (see part 8.4)
- If the stem is removed, a portion of bone at the interface with stem should be extracted to identify the bone status at this region.
- A photographic record of the position of the removed bone and/or cartilage removed will be performed before retrieval.

7. Photographic record of the explanted device and tissues,

• A photographic record of both the retrieved components (humeral head or stemmed component) and any tissues/bone dissections should be performed immediately after revision surgery. This can be done after the scrub nurse has wiped the components free of excess blood and passed them from the sterile field-ideally onto a tray covered with a clean surgical towel. A surgery label as used with tissue specimens (i.e., showing the patient ID/number, date, etc.) should be photographed at the beginning of the series and included in the photos where possible. One photo should be taken at a magnification that allows all of the removed components to be viewed together, and subsequent photos should be taken of individual components at a magnification that allows their features to be clearly seen, including the laser markings and any obvious wear or damage to the parts. The retrieved components should be photographed on both sides.

8. Containing, labeling, cleaning, decontaminating, packaging and shipping of retrieved implant, tissue, or fluid samples,

8.1. Labeling the explanted materials for future identification

- Stem and head are laser etched, so there is no need to affix a label to it. Nevertheless, each component or tissue removed from the patient will be sealed in a container that is subsequently labeled with the following information:
 - Patient ID number
 - Date explanted
 - Surgeon name
 - Hospital name

8.2. Documentation

- Documentation must accompany the explanted materials to assist Tornier with identification of the retrieved materials. Please see Section 5 for additional information on what must be recorded and documented.
- Documentation shall begin when the implant is recovered and continue until examination and analysis is complete.
- Treat the documented information as Confidential.
- The following procedure should be used for recording retrieval information:
 - Record the cleaning and sterilizing method used to decontaminate the material. Please see section 8.3 for details on how to perform these activities.
 - Record the name of the shipping service (i.e. postal service, courier, etc.), shipping number, date of shipment, and time of release.
 - If the surgical implant is to be stored prior to shipment, record the storage location.
 - The documentation shall reflect the names of all responsible individuals handling the implant during retrieval and preparation for shipping, as well as any activities performed in conjunction with its handling.

8.3. Cleaning and Decontamination/Sterilization

Clean and decontaminate/sterilize the explanted system component(s) recovered in accordance with your facility's best and safe practices for analysis prior to shipment and examination by Tornier.

The following cleaning and decontaminate/sterilize methods are recommended by Tornier for the individual system components:

- Cleaning method:
 - Intense water rinse
 - 70 % to 80 % aqueous ethanol or isopropanol rinse with subsequent ultrasonic treatment or proteolytic enzyme or 1:100 solution sodium hypochlorite
- Decontaminating and sterilizing method of components and tissues:
 - When decontaminating/sterilizing the explanted components, they should be done so in a manner that does not alter features or surfaces which may be essential in determining failure modes. In consequence, cold sterilization techniques are recommended. The explanted components should be placed into separate plastic containers filled with 10% neutral buffered formalin to at least twice the volume of the implant. The containers

must each have a standard surgical specimen label showing the medical record number, date of procedure, surgeon, and the patient number. The member of the surgical staff who provides this container and receives the specimen should write the description of the individual specimens on the individual container (for example: 'Removed Humeral Head', or 'capsule fragment 1 out of 2').

- Extracted tissues (bone, cartilage and capsule) should be placed into separate plastic containers filled with 10% neutral buffered formalin to at least twice the volume of the tissue. If important black color is detected (presence of wear particles), additional portions of tissues should be extracted and placed into glutaraldehyde, usually as a 2.5% solution in phosphate buffered saline). The containers must each have a standard surgical specimen label showing the medical record number, date of procedure, surgeon, and the patient number. The member of the surgical staff who provides this container and receives the specimen should write the description of the individual specimens on the individual container.
- A period of 24 hours is sufficient for explants with no or minimal tissue adherence, but specimens with substantial amounts of adherent bone (for example end-plate components), or tissue of a larger volume will require more time in formalin. Formalin does not adversely affect the subsequent analysis of the surface, so for all explants (tissue, implant), a permanent storage in formalin will be used to store and transport the samples.
- Note: Other methods of sterilization such as autoclaving are forbidden as they might result in irreversible damage in the form of permanent adherence of residual blood or fluids, and will render adherent tissues unsuitable for subsequent histological analysis.
- Care should be taken during any subsequent handing of the specimens to avoid damage to the parts such as rubbing the articulating surfaces together, dropping or knocking the parts or allowing tissue attached to the implants to dry out.

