After pull out, the components are gently dried, with particular care to not touch area of possible fretting corrosion (area of contact between Pyrocarbon bearing surface and CoCr double taper neck)

Step 2: General visual inspection of the components.

The goal of this first step of visual inspection is to determine, before any further manipulation of the device, if there is the presence of wear, scratching, cracking or fretting/corrosion between Pyrocarbon bearing surface and CoCr double taper neck. The 2 retrieved components (Pyrocarbon bearing surface and CoCr double taper neck) will be examined on all surfaces. For detailed exam mapping, the schematic images should include a number of views of the components, including top and bottom views, with clear identification of areas of interest, such articular wear, transitional wear zones, light scratching, heavy scratching, cracking, substrate (graphite) exposure or wear-through, embedded particles, impingement, corrosion of either articular or modular surface, contamination/discoloration/staining areas, backside wear, front face/rim wear, surface pitting, taper wear/corrosion, tribochemical layers, etc. The above schematic images should be accompanied by a series of SEM images of areas of interest, importantly, Version 2 FINAL

TORNIER (P) TORNIER (P) #15A-T-PYC-R

showing the location of where the images were taken. When pictures show some deposit on the surface, EDX exam will be executed to determine what is the physical nature of this deposit.

A particular attention will be paid to fretting-corrosion phenomenon, and the use of the scoring method described in Goldberg et al [1]. The grading will allow to graduate between 1 (none) to 4 (severe) the corrosion and fretting of the different parts as follows:

- None (score 1): No visible corrosion observed. No visible signs of fretting observed
- Mild (score 2) : <30% of taper surface discolored or dull. Single band or bands of fretting scars involving three or fewer machine lines on taper surface.
- Moderate (score 3) : >30% of taper surface discolored or dull, or <10% of taper surface containing black debris, pits, or etch marks. Several bands of fretting scars or single band involving more than three machine lines.
- Severe (score 4) : >10% of taper surface containing black debris, pits, or etch marks. Several band of fretting scars involving several adjacent machine lines, or flattened areas with nearby fretting scars.

Five scores will be established:

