
- One score for the morse taper of the CoCr double taper neck which was in connection with the stem (metal/metal connection);
- One score for the other morse taper of the CoCr double taper neck (which was in connection with the Pyrocarbon bearing surface);
- One score for the surface of the CoCr double taper neck which was in contact with the Pyrocarbon bearing surface (disk shaped surface);
- One score for the surface of the Pyrocarbon bearing surface which was in contact with the CoCr double taper neck surface (disk shaped surface);
- And one score for the female morse taper the Pyrocarbon bearing surface.

For the contact between Pyrocarbon and metal, the philosophy of the score will be used, but slightly adapted because of the difference of material and thus the difference of phenomenon that can appear (wording slightly different as colored surface instead of discolored surface).

Pyrocarbon bearing surface will thus benefit of 2 scores. CoCr double taper neck will benefit of 3 scores. All scores will be documented and reported with appropriate pictures.

Parts being scored at 1 (no corrosion) will proceed to step 3, and parts scored from 2 to 4 at even only one of their score will proceed to step 3' for quantification and qualification of metallic deposits on the parts.

11. Analysis of retrieved components and records – stage 2: physical analysis,

Step 3: Cleaning of parts having no fretting corrosion phenomenon.

Parts not featuring signs of fretting will be cleaned by ultrasonic bath in alcohol for 15mn, for future physical exams (step 4).

Step 3': Quantification of the fretting corrosion deposits on the components.

Parts being scored 2 to 4 at the fretting-corrosion scoring of step 2 will be treated as follows.

The aim of this study is to quantify the metals residue that can be found on the two components of the Aequalis[™] Pyrocarbon Humeral Head after implantation. The metals to be quantified are those produced by the possible damage of the CoCr double taper neck material, and visualized by EDX probe at step 2, i.e. Cobalt, Chromium,

Manganese, Nickel and Molybdenum.

Each item is soaked in 50 ml of water and sonicated for 210 minutes, the solution is then diluted 1:2 and 1:10 to obtain values that fall into the range of the available standards for all the investigated metals. Solutions are evaluated by ICP-MS, and quantity of metal expressed in μ g/component.

Step 4: surface roughness measurement on Pyrocarbon bearing surface

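### Appendix 4 recommends cleaning explants at the hospital, with ultrasound as an option, before the laboratory scores corrosion and assays metal residue; exposed surfaces could then read low

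*Protocol*

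**What the plan says.** Section 8.3 of Protocol Appendix 4 asks the hospital to clean and decontaminate explanted components "for analysis prior to shipment and examination by Tornier". It refers to the facility's own good practice and then lists cleaning "methods are recommended by Tornier for the individual system components": an intense water rinse, followed by "70 % to 80 % aqueous ethanol or isopropanol rinse with subsequent ultrasonic treatment or proteolytic enzyme or 1:100 solution sodium hypochlorite". A separate bullet on decontamination asks for cold methods, "in a manner that does not alter features or surfaces which may be essential in determining failure modes", and places components in 10% formalin. The same section bans autoclaving, partly because it "will render adherent tissues unsuitable for subsequent histological analysis".

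The laboratory work follows in sections 10 and 11:

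- **Step 1** pulls the head off the stem if they are still joined, then separates the bearing surface from the neck.
- **Step 2** inspects and scores fretting and corrosion: "The goal of this first step of visual inspection is to determine, before any further manipulation of the device". Surface deposits go to EDX.
- **Step 3** is for parts with no corrosion: "Parts not featuring signs of fretting will be cleaned by ultrasonic bath in alcohol for 15mn".
- **Step 3'** is for parts with any score from 2 to 4: "Each item is soaked in 50 ml of water and sonicated for 210 minutes". The solution is assayed by ICP-MS and reported in micrograms per component.

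**The concern.** The appendix uses ultrasound in two ways. In Step 3 it is a cleaning method, applied after scoring and only where there is nothing to preserve. In Step 3' sonication puts the residue into solution so that it can be measured. Section 8.3 offers ultrasound to the hospital ahead of both. Residue released there goes out with the cleaning liquid, which nobody assays.

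Retrieval analysis is the plan's route to the mode and cause of device failure (Appendix 4, section 13). Residue removed before Step 2 could lower a corrosion score, leave EDX with nothing to identify, or reduce the metal measured in Step 3'. Each of these would make the device look cleaner than it was in the body, and the material cannot be recovered.

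**Working it through.** No figure in the plan needs reproducing. The check is of order and exposure.

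**1. Order of handling as written**

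| Order | Place | Action | Source (Appendix 4) |
|---|---|---|---|
| 1 | Hospital | Water rinse; alcohol rinse; ultrasound, enzyme or hypochlorite | 8.3 |
| 2 | Hospital | Formalin, packing, shipment | 8.3, 8.4 |
| 3 | Laboratory | Pull-out tests | 10, Step 1 |
| 4 | Laboratory | Visual scoring, EDX on deposits | 10, Step 2 |
| 5a | Laboratory | Parts scored 1: ultrasonic alcohol bath | 11, Step 3 |
| 5b | Laboratory | Parts with any score of 2 to 4: sonication and ICP-MS | 11, Step 3' |

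Nothing in the appendix requires scoring before row 1 or exempts possible fretting areas from it. Yet between rows 3 and 4 laboratory staff are told to avoid even touching those areas while drying the parts.

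**2. Which surfaces are exposed at row 1**

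The head is joined at manufacture and cannot be taken apart by the user (Protocol 4.1). Bearing surface and neck separate only at Step 1 in the laboratory. Step 2 gives five scores:

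| Scored surface | During hospital cleaning |
|---|---|
| Neck, stem-side taper | Exposed if the head was taken off the stem; enclosed if head and stem came out joined |
| Neck, taper into the bearing surface | Enclosed |
| Neck, disk face | Enclosed |
| Bearing surface, disk face | Enclosed |
| Bearing surface, female taper | Enclosed |

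So 4 of 5 scored surfaces are enclosed and 1 of 5 may be exposed. Removal of the head from the stem at surgery is foreseen: section 4.2 of the appendix has the surgeon mark the neck first, and Step 1 covers heads retrieved separately. The outer surfaces are also exposed. They carry none of the five scores, but Step 2 maps staining and embedded particles on all surfaces.

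**3. How a reading could change**

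- *Score.* Black debris helps define scores 3 and 4. So do pits and etch marks, and discoloration and fretting scars count as well. Removing debris lowers a score only where debris was what raised it.
- *Routing.* The bearing surface has two scores, both on enclosed surfaces. The neck has three. For a neck to miss Step 3' through this route, both enclosed surfaces must score 1 and the stem-side taper must have shown only removable signs.
- *Assay.* Step 3' soaks the whole item. Residue already lost from any exposed surface lowers the total even when routing is correct.

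**4. How many retrievals are at stake**

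Inputs: 157 implant attempts (Protocol 13.2.2); 10 of 191 revised within 24 months in the Aequalis data, and the 13.2% revision limit (both SAP 12.6).

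- 157 × 10/191 = 8.2, about 8 subjects
- 157 × 0.132 = 20.7, about 21 subjects

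These are revisions. Under Protocol 7.7 a revision may only reposition or adjust the implant, so not every one yields an explant.

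**The case against.** The case against has considerable force.

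- Most scored surfaces are shielded, and the area the protocol names as the likely site of fretting is the contact between bearing surface and neck, which is enclosed. The documents do not say whether fluid enters that junction. This stands and narrows the point to the stem-side taper of heads removed separately, outer-surface deposits and the whole-item assay.
- Scars, pits and etch marks also drive the scores, and nothing in the documents says that ultrasound removes them. This stands. A reader might infer that corroded parts will generally be passed as clean; the routing rule and the other scoring signs do not support that.
- Section 8.4 packs parts already cleaned, and Step 2 speaks only of further manipulation, so the laboratory may not expect untouched parts. That is fair, but it does not explain why Step 3 withholds ultrasound from fretted parts if every part may already have had it.
- Section 8.3 gives no duration or intensity, makes ultrasound one of several options and only recommends it, whereas Step 3' runs for 210 minutes. Hence residue can be lost; that it will be lost does not follow.
- A reader might also infer that histology is compromised. Capsule, cartilage and bone samples are taken separately and fixed, outside the component cleaning bullet. Only tissue adhering to the implant is in question, and the documents state no effect of enzyme or hypochlorite on it or on deposits.
- Photographs after surgery (section 7), the record of the cleaning method (section 8.2) and the clause on preserving surfaces all help. But photographs cannot replace EDX or ICP-MS, a record restores nothing, and the clause sits under decontamination rather than cleaning.

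**Conclusion.** Section 8.3 and Steps 2, 3 and 3' of Appendix 4 conflict on when ultrasound may be applied to an explant. Followed as written, the hospital step can remove residue from exposed surfaces before scoring, EDX and the metal assay, which could bias those readings low.

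The ultrasound part rests on the appendix's own use of it in Steps 3 and 3'. Any effect of enzyme or hypochlorite is inference. The conclusion assumes that some heads are removed from the stem before cleaning and that some hospitals choose ultrasound. The size of the loss is unknown.

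It would be wrong to carry this over to the trial's conclusions. No primary or secondary endpoint uses retrieval results, so sample size, the primary test and the secondary tests are unaffected. What is at risk is failure-mode evidence from a small number of explants, where each one counts.

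**What to change.** In Appendix 4, section 8.3, limit pre-shipment handling of components to the water rinse already listed and the 10% formalin fixation and transport already required. Move the ultrasonic option to after Step 2 and, for parts scored 2 to 4, after Step 3'. Move the enzyme and hypochlorite options with it, unless the sponsor shows that they leave deposits and adherent tissue unaffected. Align section 8.4, which refers to cleaned components, and the return instructions. If a hospital's own rules require more, the record under section 8.2 should say so, so that the laboratory can read that part's results accordingly.

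The cost is mainly wording. The laboratory would receive formalin-fixed rather than pre-cleaned parts, a small burden given that section 8.3 itself states that formalin does no harm to later surface analysis.
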